Ciprofloxacin Versus Levofloxacin in Stem Cell Transplant

NCT03850379

Study protocol March 14, 2018

4. **SIGNIFICANCE:** State concisely the importance of this project by relating the purpose to broader, long-range objectives. This selective intervention will establish a unique setting to assess the efficacy of the use of levofloxacin vs ciprofloxacin prophylaxis in patients undergoing SCT

5. **SUBJECTS IN THE PROJECT:**

- State the inclusion and exclusion criteria for enrollment of subjects. **Eligibility Criteria:** Patients 18-75 years of age with a diagnosis of a hematological malignancy. Meet the BMT program criteria to undergo hematopoietic stem cell transplantation.
- Describe the control population (if utilized) and justify its selection. **NA**
- Support the likelihood of recruiting the number of subjects required to complete the project. Relate this to other projects recruiting similar subjects. In our growing program we have been doing almost 100 SCT per year and all need prophylaxis antibiotics to prevent infection

6. **PROJECT DESIGN AND PROTOCOL:**

- Describe the experimental design/methodology. This is a prospective study comparing consecutive patients who will be receiving ciprofloxacin prophylaxis vs. levofloxacin prophylaxis for SCT till engraftment defined as ANC >1000,
- Outline the protocol, corresponding it to the specific aims; identify the data or endpoints to be analyzed to reach the specific aims. **Primary Objective:** to assess incidence of bloodstream bacterial infections in the ciprofloxacin group compared to levofloxacin group up to day 60 after SCT. **Secondary objectives:** To assess time to engraftment, incidence of Clostridium difficile infection, rate of febrile neutropenia, Incidence of Gram positive and gram negative bacterial breakthrough infections, inpatient mortality, rate of hypotension, ICU admissions, fungal infections. In allo SCT patients assess rate of acute graft versus host disease (GVHD) by day 60. Blood stream infections will be documented along with type of pathogen and drug resistance. Also C diff infection will be documented. Time of engraftment will be documented. Secondary objectives like GVHD, PFS, OS will be assessed using this regimen. PFS and OS were estimated from day 0 according to the Kaplan-Meier method. Estimates of treatment related mortality, acute GVHD and chronic GVHD rates will be based upon cumulative incidence estimates, treating relapse as a competing risk. Engraftment rates (and corresponding 95% confidence intervals) will be estimated by the proportion of patients who engraft. Neutrophil recovery is defined as a sustained absolute neutrophil count (ANC) > 0.5 x 10⁹/L for 3 consecutive days. Engraftment date is the first day of three (3) consecutive days that the ANC exceeds 0.5 x 10⁹/L. Delayed engraftment is defined as the evidence of engraftment beyond day 28 post SC infusion achieved after the administration of therapeutic (high dose) hematopoietic growth factors. Primary Graft failure is defined as failure to achieve an ANC > 0.5 x 10⁹/L for 3 consecutive days by day 28 post SC infusion, with no evidence of donor derived cells by bone marrow chimerism studies and no evidence of persistent or relapsing disease. Secondary graft failure is defined as a sustained decline of ANC < 0.5 x 10⁹/L for 3 consecutive days after initial documented engraftment with no evidence of disease progression. Autologous reconstitution is defined by the presence of ANC > 0.5 x 10⁹/L without evidence of donor-derived cells by bone marrow chimerism studies. This can occur at initial engraftment or later after initial engraftment has been documented. Complete remission (CR) is defined according to disease specific criteria as per the CIBMTR. Relapse defined according to disease specific criteria will be recorded by the day of detection.
- Discuss potential limitations and difficulties in the protocol. Uncontrolled multi-variables and their contribution to patient's disease course may attenuate the results. Sorting and stratifying each variable may create multiple small groups of patients which may not possess the power to reflect and determine differences among those small groups
- Provide a tentative schedule for conducting and completing this project and, if applicable, the multicenter study. We do around 100 SCT per year, so we will need 3 years to recruit the patients and 4 years to finalize the data
- Data collection: Submit a copy of the data collection tool or list the data fields to be collected (review IRB policy, *Access to Medical Records for Research*). attached

7. **DATA ANALYSIS:** Describe the analysis of the data and relate this to the specific aims in detail. Case reports and medical record reviews also require a description of the planned data analysis (ie. descriptive, observational). The Committee recommends free consultation with the Division of Biostatistics and Research Epidemiology before IRB submission. **Number of pts needed:** to prove 10% improvement in overall bacterial infections control (Decrease from 20% to 10%), need 308 pts; 154 in each group To achieve 70% power. Data will be collected and analyzed. We will prospectively follow patients who will get

HSCT. Objectives are to explore the impact of cipro vs levo on Incidence of bacteremia and incidence of resistant and non-resistant gram-positive strains bacteremia. Also impact of Levo vs Cipro incidence of Clostridium difficile and GVHD Demographics, disease-related and transplant-related variables mentioned above will be collected. A two sample test of proportion equality will be used as the test for the primary aim. PFS is defined as the time from HSCT to the time of progression, death or last contact whichever occurred first. OS is defined as the time from HSCT to the time of death or last contact. OS and PFS will be estimated using the Kaplan-Meier method.

8. JUSTIFICATION FOR NUMBER OF SUBJECTS OR DATA:

- State the number of subjects or data points to be analyzed in the project at this institution and the total number for multicenter studies. The Committee recommends consultation with the Division of Biostatistics and Research Epidemiology [contact]. 2. The target sample size is 308 patients. Accrual Period: 3 years.
- Describe the statistical justification for this number of subjects or data points. after discussion with biostat to calculate Number of pts needed: to prove 10% improvement in overall bacterial infections control (Decrease from 20% to 10%), need 308 pts; 154 in each group To achieve 70% power.*

FORM A

HENRY FORD HEALTH SYSTEM (IRB) DRUG/SUBSTANCE INFORMATION

(This form must be completed for each individual drug or substance -*investigational or marketed*- that is being administered as part of this research study)

1. Generic/Chemical Name: Ciprofloxacin	2. Trade Name: Cipro
3. Manufacturer: Bayer	4. Mode of Administration: P.O. other: IV
5. How Supplied (dose form & strength): 500 mg	6. Who will be administer the drug/substance? P2 Nurse
7. Dosage and Schedule Proposed: 500 mg BID	
8. Will you be utilizing research pharmacy for storage or dispensing of any medication? (if this is an inpatient study, you are required to use research pharmacy).  Yes  No	
9. Describe the primary actions of the drug/substance: Prevnet infections in neutropenic patients by Inhibiting DNA-gyrase in susceptible organisms	
10. Describe the therapeutic benefit anticipated from the use of this drug/substance: Prevent infections in neutropenic patients after the conditioning regimen for SCT	
11. List the known side effects (these should also be listed in the consent form in this manner): 
 ✓ Likely: none ✓ Less likely: headache ✓ Skin rash (1%) ✓ Diarrhea (2%), vomiting (1%), abdominal pain (<1%), nausea (3%) ✓ Increased liver enzymes AST (1%) ✓ Fever (<1%) ✓ Rare, but serious: <1% : severe allergic reaction with low blood pressure and difficulty breathing, Clostridium difficile-associated diarrhea, confusion, convulsions, decreased visual acuity, depression, liver failure, peripheral neuropathy (may be irreversible), abnormal heart conduction on ECG, rupture of tendon, inflammation in pancreas , low counts 	
12. Describe the precautions used to insure that the risks associated with the administration of this drug/substance is minimized: toxicities will be monitored and dosage will be modified per BMT protocol	

 Yes  No	13. Are there special storage safety or handling conditions required? If yes, please describe:
 Yes  No	14. Is there an IND #? If 'yes', is this an (check which one applies):  investigational drug/substance  approved drug being investigated to provide data to the FDA in support of a new indication or to change the labeling
 Yes  No	15. Have restrictions been placed on the use of this drug/substance by the FDA? If yes, describe them: Fluoroquinolones have been associated with disabling and potentially irreversible serious adverse reactions that have occurred together, including: tendinitis and tendon rupture, peripheral neuropathy, and CNS effects. Discontinue ciprofloxacin immediately and avoid the use of fluoroquinolones in patients who experience any of these serious adverse reactions.
 Yes  No	16. Are other drugs/substances known to interact in important ways with the investigational agent being tested in this protocol? If yes, list the drugs/substances (and/or their categories) and describe the precautions for avoiding adverse events resulting from such interactions: Fluoroquinolones may prolong QTc Interval same as antifungal azoles but we assess ECG and QT Interval in all out SCT pts and use alternatives when QT is prolonged
 Yes  No	17. Is the drug/substance to be used in children? If yes, has it been approved for use in these subjects?
 Yes  No	18. Is the drug/substance to be used in pregnant women? If yes, has it been approved for use in these subjects?
 Yes  No	19. Will the dosage/schedule be modified within the protocol in response to efficacy or side effects? If yes, what end points will drive the dosage alterations? drug will be discontinued and alternative prophylaxis will be used in the event of unacceptable toxicity per our ID transplant protocol Azithromycin 250 mg PO QD
 Yes  No	20. Is compliance with dosage schedule monitored? If yes, how? P2 nurse giving the medication and documenting in MAR
 Yes  No	21. Is this a blinded study? If yes, describe the provisions that have been made for breaking the code in the event of a significant adverse event?
 Yes  No	22. Have provisions been made for "after hours" or holiday availability of the PI or Co-PI for consultation? If yes, describe them: the PI and co -investigators will be on call on a continual basis while patients are treated on this stud

FORM B

HENRY FORD HEALTH SYSTEM IRB MEDICAL DEVICE INFORMATION

(This form must be completed for each individual device -investigational or marketed- which is being used as part of this research study)

1. Name of Device:
2. Manufacturer:
3. Marketed?  Yes  No (If 510K received, include FDA documentation)
4. Investigational?  Yes  No If yes, IDE#: (include FDA IND letter)
5. What is the sponsor's or FDA's risk determination for this study?  Significant Risk Device Study  Nonsignificant Risk Device Study

FORM A

HENRY FORD HEALTH SYSTEM (IRB) DRUG/SUBSTANCE INFORMATION

(This form must be completed for each individual drug or substance -*investigational or marketed*- that is being administered as part of this research study)

1. Generic/Chemical Name: Levofloxacin	2. Trade Name: Levaquin
3. Manufacturer: Janssen	4. Mode of Administration: P.O. other:
5. How Supplied (dose form & strength): tablet 500 mg	6. Who will be administer the drug/substance?
7. Dosage and Schedule Proposed: 500 mg once daily	
8. Will you be utilizing research pharmacy for storage or dispensing of any medication? (if this is an inpatient study, you are required to use research pharmacy).  Yes  No	
9. Describe the primary actions of the drug/substance: inhibits DNA-gyrase in susceptible organisms thereby inhibits relaxation of supercoiled DNA and promotes breakage of DNA strands to help prevent infections	
10. Describe the therapeutic benefit anticipated from the use of this drug/substance:	
11. List the known side effects (these should also be listed in the consent form in this manner):  Likely: none  Less likely: Chest pain (1%), edema (1%)  Headache (6%), insomnia (4%), dizziness (3%)  Skin rash (2%), itching (1%)  Nausea (7%), diarrhea (5%), constipation (3%), abdominal pain (2%), vomiting (2%)  Vaginal itching (1%)  Infection with candida (1%)  Difficulty breathing (1%)  Rare, but serious: <1% : severe allergic reaction with low blood pressure and difficulty breathing, Clostridium difficile-associated diarrhea, confusion, convulsions, decreased visual acuity, depression, liver failure, peripheral neuropathy (may be irreversible), abnormal heart conduction on ECG, rupture of tendon, inflammation in pancreas, low counts	
12. Describe the precautions used to insure that the risks associated with the administration of this drug/substance is minimized: , toxicities will be monitored and dosage will be modified per BMT protocol	
 Yes  No	13. Are there special storage safety or handling conditions required? If yes, please describe:
 Yes  No	14. Is there an IND #? If 'yes', is this an (check which one applies):  investigational drug/substance  approved drug being investigated to provide data to the FDA in support of a new indication or to change the labeling
 Yes  No	15. Have restrictions been placed on the use of this drug/substance by the FDA? If yes, describe them: Fluoroquinolones are associated with disabling and potentially irreversible serious adverse reactions that may occur together, including tendonitis and tendon rupture, peripheral neuropathy, and CNS effects. Discontinue levofloxacin immediately and avoid use of fluoroquinolones in patients who experience any of these serious adverse reactions.
 Yes  No	16. Are other drugs/substances known to interact in important ways with the investigational

	agent being tested in this protocol? If yes, list the drugs/substances (and/or their categories) and describe the precautions for avoiding adverse events resulting from such interactions: Fluoroquinolones may prolong QTc interval same as antifungal azoles but we assess ECG and QT interval in all out SCT pts and use alternatives when QT is prolonged
 Yes  No	17. Is the drug/substance to be used in children? If yes, has it been approved for use in these subjects?
 Yes  No	18. Is the drug/substance to be used in pregnant women? If yes, has it been approved for use in these subjects?
 Yes  No	19. Will the dosage/schedule be modified within the protocol in response to efficacy or side effects? If yes, what end points will drive the dosage alterations? drug will be discontinued and alternative prophylaxis will be used in the event of unacceptable toxicity per our ID transplant protocol Azithromycin 250 mg PO QD
 Yes  No	20. Is compliance with dosage schedule monitored? If yes, how? P2 nurse giving the medication and documenting in MAR
 Yes  No	21. Is this a blinded study? If yes, describe the provisions that have been made for breaking the code in the event of a significant adverse event?
 Yes  No	22. Have provisions been made for "after hours" or holiday availability of the PI or Co-PI for consultation? If yes, describe them: the PI and co -investigators will be on call on a continual basis while patients are treated on this study

DO NOT SUBMIT THIS FORM IF YOU ARE NOT USING A DRUG/SUBSTANCE IN THIS STUDY

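### Do the two uses of the word engraftment in section 6 leave the secondary engraftment endpoints undefined?

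*Combined protocol and SAP*

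**What the plan says.** Two places in section 6 matter.

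- **Experimental design sentence.** Consecutive patients receive one drug or the other, and prophylaxis ends at a count criterion: "levofloxacin prophylaxis for SCT till engraftment defined as ANC >1000". No unit and no number of days are visible. The sentence breaks off at a comma, so some text may be lost, and the missing unit is not held against the plan.
- **Protocol outline and endpoints.** The secondary objectives begin "To assess time to engraftment, incidence of Clostridium difficile infection". The rate is planned as follows: "Engraftment rates (and corresponding 95% confidence intervals) will be estimated by the proportion of patients who engraft". The definitions come next: "Neutrophil recovery is defined as a sustained absolute neutrophil count (ANC) > 0.5 x 10⁹/L for 3 consecutive days", then "Engraftment date is the first day of three (3) consecutive days that the ANC exceeds 0.5 x 10⁹/L". Primary graft failure and autologous reconstitution use the same 0.5 threshold. A further category reads "Delayed engraftment is defined as the evidence of engraftment beyond day 28 post SC infusion", and the sentence goes on to require that this followed high-dose growth factors.

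For the primary aim, section 7 (Data Analysis) says: "A two sample test of proportion equality will be used as the test for the primary aim".

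**The concern.** The design sentence does more than name a stopping threshold: it presents ANC >1000 as the definition of engraftment. A few lines later the same word gets another threshold and a three-day requirement. No visible sentence says that the two are separate concepts. Three items in the endpoint text (the engraftment rate, delayed engraftment and secondary graft failure) use the word without repeating a threshold.

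If an analyst carried the first definition into those items, time to engraftment could shift by days, and some patients could change between engrafted and not engrafted. The choice could then be made after seeing the data. That would be a real weakness if the text left the choice open.

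**Working it through.** **1. The plan's own figure, and whether it depends on engraftment.** The inputs are in sections 7 and 8: 20% versus 10%, 70% power, 154 per group. Alpha is not stated; 0.05 two-sided is assumed.

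- Arcsine formula: h = 2·asin(√0.20) − 2·asin(√0.10) = 0.9273 − 0.6435 = 0.2838. Then n = 2·((1.960 + 0.524)/0.2838)² ≈ 153.3, rounded up to 154 per group, **308** in total. This reproduces the plan exactly.
- Unpooled normal formula: (1.960 + 0.524)²·(0.16 + 0.09)/0.01 ≈ 154.3, rounded up to 155 per group, 310 in total.

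The inputs are infection proportions up to a fixed day 60. No engraftment date or status enters the endpoint, its test or the sample size.

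**2. The two criteria side by side.**

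| | Design sentence | Endpoint text |
|---|---|---|
| Threshold | >1000 (1.0 x 10⁹/L if cells/µL, assumed) | >0.5 x 10⁹/L |
| Days required | none stated | 3 consecutive |
| Rule for the date | none | first of the 3 days |
| Use in the text | length of prophylaxis | definitions beside the endpoints |

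**3. Can they disagree?** Both rules were applied to four invented daily ANC series (x 10⁹/L). For the design sentence, the first day above 1.0 was taken as the date. That rule had to be supplied, because the sentence has none.

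| Series | First day >1.0 | First of 3 days >0.5 |
|---|---|---|
| Gradual, from day 10: 0.1, 0.3, 0.6, 0.7, 0.8, 0.9, 1.2, 1.5 | day 16 | day 12 |
| Plateau, from day 12: 0.3, 0.6, 0.7, 0.8, 0.7, 0.8, 0.9, 0.8 | not reached | day 13 |
| One-day peak, from day 10: 0.2, 0.4, 1.1, 0.4, 0.3, 0.2, 0.4, 0.3 | day 12 | not reached |
| Steep, from day 10: 0.1, 0.2, 1.1, 1.6, 2.0, 2.5, 3, 3 | day 12 | day 12 |

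So the rules can disagree on date and on status, though not always. The remaining question is whether the plan leaves it open which one serves the endpoints.

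**4. Each engraftment item, read in place.**

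- *Time to engraftment.* The endpoint text supplies an explicit date rule, and it is the only one in the document.
- *Engraftment rate.* The sentence is followed directly by the 0.5 definitions of neutrophil recovery and engraftment date.
- *Primary graft failure.* It is failure to hold 0.5 for three days by day 28. With >1000 as the meaning of engraftment, a patient steady at 0.6 to 0.9 would be neither engrafted nor a primary failure. At 0.5 that gap in the count criterion closes.
- *Secondary graft failure.* It depends on initial engraftment. The autologous reconstitution definition uses ANC >0.5 and says this can happen at initial engraftment, which ties that phrase to 0.5.
- *Delayed engraftment.* It shares the day-28 line with primary graft failure, which uses 0.5. It also needs prior growth-factor treatment. A patient above 0.5 from day 24 and above 1.0 only on day 30 is therefore not moved into this category by the date alone.
- *End of prophylaxis.* Only the design sentence states it. No other place gives a different end, and the sentence covers both groups.

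**5. Size if the wrong reading were used.** One patient moves a group's proportion by 1/154 = 0.65 points. For scale, take a Wald interval with 154 patients, half-width 1.96·√(p(1−p)/154), at assumed proportions:

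- p = 0.90: 4.74 points, equal to 7.3 patients
- p = 0.95: 3.44 points, equal to 5.3 patients
- p = 0.98: 2.21 points, equal to 3.4 patients

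It would take 8, 6 or 4 patients in one group to shift the estimate by a full half-width. This is a break-even figure, not an estimate: the documents give no ANC data, name no interval method, and do not say that the rate is reported by group. The rate also has no visible time limit, so crossing 1000 late changes a date but not the proportion. Only patients who never exceed 1000, or who peak without sustaining 0.5, would change status.

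**The case for a change.** The best case for a change is that definitions should not rest on a natural reading. The design sentence is worded as a definition, nothing visible restricts it to prophylaxis, and staff may record as the engraftment date the day on which prophylaxis stopped. The data collection tool is attached to the protocol but not reproduced here, so its date field cannot be compared with the endpoint rule. A clarification would cost one sentence and is best made before the data are seen.

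Part of this stands. One word does carry two meanings, and the two passages need to be reconciled in wording, whichever way the sponsor intends them. The inability to check the tool also stands, but it cuts both ways: the tool, or text lost after the comma, may already separate the two uses.

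What does not stand is that the plan leaves the endpoints open. To get a second engraftment date, an analyst must invent a date rule for the design sentence and disregard the one written beside the endpoints.

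**Conclusion.** The concern does not call for a change to the plan. The inconsistency is one of terminology: the end-of-prophylaxis criterion borrows the name of an endpoint that is defined separately and consistently. Both statements can be followed together, one for how long prophylaxis lasts and the other for the engraftment date and status. Followed that way, the engraftment results are sound.

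The effect on the primary endpoint, its test and the 308 patients is nil. No bias between groups is shown, because the same wording applies to both. For the secondary engraftment endpoints the effect is nil under the reading that the text supports. Under the other reading it would be 0.65 points per reclassified patient in a group, with a number of patients that the documents do not allow anyone to estimate.

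This rests on two assumptions: that 1000 means cells per microlitre, and that the unseen data field follows the written date rule. The three-day difference between the criteria does not depend on the unit. A clause separating the two uses would be good housekeeping if the protocol is reopened, but it would change no result. No view is taken here on which count should end prophylaxis.

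### The competing-risk rule for acute and chronic GVHD names only relapse; death without GVHD is left out, and applying the rule as written overstates GVHD incidence

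*Combined protocol and SAP*

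**What the plan says.** The estimation rule is in section 6 (Project design and protocol): "Estimates of treatment related mortality, acute GVHD and chronic GVHD rates will be based upon cumulative incidence estimates, treating relapse as a competing risk". It covers three endpoints and names one competing event.

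The same section sets the acute GVHD objective, its population and its horizon: "In allo SCT patients assess rate of acute graft versus host disease (GVHD) by day 60". Section 7 (Data analysis) lists a comparison between the drugs among the objectives to explore: "Also impact of Levo vs Cipro incidence of Clostridium difficile and GVHD". Chronic GVHD appears by name only in the estimation rule, and no horizon is given for it.

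Apart from treatment-related mortality, death appears in three places. Section 6 lists it among the secondary objectives: "inpatient mortality, rate of hypotension, ICU admissions, fungal infections". Section 7 uses it in the two survival definitions: "PFS is defined as the time from HSCT to the time of progression, death or last contact whichever occurred first" and "OS is defined as the time from HSCT to the time of death or last contact". None of these says how a death before GVHD is handled when GVHD incidence is estimated.

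**The concern.** A competing event is one after which the event of interest can no longer occur. For treatment-related mortality, understood as death without relapse, relapse fills that role and no other terminal event is left over. For GVHD, death without GVHD is the clearest competing event, and it is the one not named.

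An analyst who follows the sentence as written codes GVHD as the event, relapse as competing and everything else as censored. Censoring treats patients who died as if they could still develop GVHD at the same rate as those still at risk, and this inflates the estimate. The inflation grows with the number of such deaths and with how early they occur. It does not shrink with sample size, and the confidence interval does not reflect it.

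At stake are the acute GVHD rate by day 60, any chronic GVHD rate, and the exploratory comparison of GVHD between the two drugs.

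**Working it through.** **The plan's own figures.** The plan states no figure for GVHD or for competing risks. Its one derived figure is the sample size, "to prove 10% improvement in overall bacterial infections control (Decrease from 20% to 10%), need 308 pts; 154 in each group" with the aim "To achieve 70% power". With a two-sided 5% level (assumed, as none is stated) and the unpooled formula, n per group = (1.960 + 0.524)² × (0.20×0.80 + 0.10×0.90) / 0.10² = 154.3, which agrees with 154. This point does not touch that figure.

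**Inputs.** All rates below are assumptions. By the end of the window, let c1 be the true proportion with GVHD, c2 the proportion who die without GVHD or relapse, and c3 the proportion who relapse first.
- Acute GVHD by day 60: c1 = 35%, c3 = 5%, c2 = 2%, 5% or 10%.
- Chronic GVHD, for illustration only: c1 = 40%, c3 = 15%, c2 = 10%, 15% or 20%.

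**Step 1: proportional cause-specific hazards.** Let T = c1 + c2 + c3 and H = −ln(1 − T). With relapse competing and deaths censored,

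reported = c1/(c1 + c3) × [1 − exp(−H × (c1 + c3)/T)].

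Example with c2 = 5%: T = 0.45, H = 0.598, (c1 + c3)/T = 0.40/0.45 = 0.889, so reported = 0.875 × [1 − exp(−0.531)] = 0.875 × 0.412 = 0.3607. The excess is 1.1 points.

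**Step 2: timing of deaths.** GVHD and relapse are spread evenly over the window, and deaths fall evenly over its first half, all of it, or its second half. The reported incidence is then integrated numerically, using the true GVHD and relapse hazards but a survival function that ignores deaths. The whole-window results match step 1.

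**Step 3: bounds over any timing.** The excess is zero if all such deaths come after all GVHD and relapse. It is largest if relapses come first, then deaths, then GVHD. Survival ignoring deaths is then 1 − c3, while GVHD occurs in c1 out of 1 − c2 − c3 still at risk. So reported = (1 − c3) × c1/(1 − c2 − c3), and the excess is c1 × c2/(1 − c2 − c3). For c2 = 5% in the acute case: 0.35 × 0.05/0.90 = 0.0194.

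Excess in percentage points:

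| Endpoint | Deaths c2 | Deaths in 2nd half | Whole window | Deaths in 1st half | Upper bound |
|---|---|---|---|---|---|
| Acute | 2% | 0.2 | 0.4 | 0.6 | 0.8 |
| Acute | 5% | 0.6 | 1.1 | 1.5 | 1.9 |
| Acute | 10% | 1.3 | 2.2 | 3.2 | 4.1 |
| Chronic | 10% | 1.8 | 2.8 | 3.9 | 5.3 |
| Chronic | 15% | 2.9 | 4.5 | 6.2 | 8.6 |
| Chronic | 20% | 4.3 | 6.4 | 8.9 | 12.3 |

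**Step 4: simulation check.** With 400,000 simulated patients, true GVHD 40%, relapse 5% and deaths 10%, the cumulative incidence estimate was 40.1% with death competing and 42.7% with death censored. The step 1 formula gives 42.6% for the second.

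**Step 5: false difference between groups, acute GVHD.** With the same true 35% in both groups:
- 5% against 7% deaths: 0.3653 − 0.3607 = 0.0046, or 0.5 points.
- 5% against 10% deaths: 0.3724 − 0.3607 = 0.0117, or 1.2 points.
- 5% deaths in both, early in one group and late in the other: 0.9 points.

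**Step 6: sampling error of that comparison.** The 95% half-width is 1.96 × √(2 × 0.35 × 0.65/n), with n allogeneic patients per group. The plan does not give the allogeneic share. The half-width is 13.0 points at two thirds (n = 103), 15.1 at one half (n = 77) and 18.5 at one third (n = 51). If all 308 were allogeneic (n = 154) it would be 10.7.

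**The case against.** The strongest reply is that the sentence is incomplete and not wrong. It calls relapse a competing risk, does not say it is the only one, and never says deaths are censored, so a competent analyst could code death as competing. This stands as a limit: the bias is conditional on a literal reading. It does not remove the problem. The sentence is the plan's only rule for GVHD, it gives a wrong result for two of its three endpoints when followed as written, and it lets two analysts report different rates from the same data.

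A second reply is that the effect is minor. For the comparison between drugs this stands: false gaps of 0.5 to 1.2 points are small beside half-widths of 13.0 to 18.5, and nothing in the document suggests that deaths will differ between groups. Section 7 names no test for GVHD. The GVHD rates are also planned as estimates in their own right, and there the bias does not average out.

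Third, every rate is assumed. That is so, and the largest figures belong to chronic GVHD, which no objective names separately. They should not carry the argument.

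Fourth, the plan counts deaths but does not show that deaths before GVHD are expected in allogeneic patients by day 60. Inpatient mortality includes autologous patients, and treatment-related mortality is undefined and could include deaths after GVHD. This is fair: how many of the recorded deaths would precede GVHD is unknown. If there were none, the bias would be zero.

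Finally, a plain day-60 proportion with complete follow-up would not have this bias. True, but section 6 specifies cumulative incidence, and chronic GVHD has no stated horizon at which to take a proportion.

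**Conclusion.** The concern holds. The plan sets one rule for three endpoints, and for acute and chronic GVHD it omits death without GVHD as a competing event. Taken literally, the rule never biases GVHD incidence downward, and it biases it upward whenever GVHD events follow such deaths.

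The document supports no specific magnitude. Under the stated assumptions and proportional hazards, the excess is about 0.4 to 2.2 points for acute GVHD at day 60 with 2% to 10% deaths. It could be larger for chronic GVHD over a longer horizon. The comparison between drugs is unlikely to be materially distorted.

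The primary endpoint, its test and the sample size are unaffected. This should be corrected, but it does not threaten the trial's main conclusion.

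**What to change.** Replace the single sentence in section 6 with one rule per endpoint, for example:

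> Treatment-related mortality will be estimated by cumulative incidence with relapse as the competing event. Acute and chronic GVHD will be estimated in allogeneic recipients by cumulative incidence, with death without GVHD (and relapse, if the sponsor keeps it) as competing events.

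The sponsor should also confirm that treatment-related mortality means death without relapse, since relapse alone is a sufficient competing event only under that definition.

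If day-60 status is complete and relapse is not kept as a competing event, the plain proportion with acute GVHD by day 60 equals the corrected estimate and can serve as a check.

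The cost is one sentence of analysis text. Death dates are already needed for OS, and section 6 already records relapse by day of detection. The data collection form is not in the available text, so its fields could not be checked, but the change needs nothing beyond what the planned endpoints already require.
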